8.2 Study Visits

8.2.1 Visit Schedule

This will be a non-dispensing study. Each subject will be required to attend one scheduled study visit over a period of approximately 3.5 hours in a single day. They will be examined at three different time-points.

First Time-point:

Screening and Enrolment:

Baseline Assessment:

1st Pair Study Lens Assessment: Insert 1st pair of study lenses, assess fit after 30 minutes then discard lenses

Second Time-point:

2nd Pair Study Lens Assessment: Insert 2nd pair of study lenses, assess fit after 30 minutes then discard lenses

Third Time-point:

3rd Pair Study Lens Assessment: Insert 3rd pair of study lenses, assess fit after 30 minutes then discard lenses and exit

Subjects may discontinue or be discontinued from the study at any time, and the Exit Visit CRF will be completed.

8.2.2 Screening and Enrolment

The following procedures will be conducted on all subjects:

- i. Allow the subject to read the Patient Information Sheet and Informed Consent Form (ICF) and explain the nature, purpose, risks of the study, etc. If they are agreeable, ask the subject to print their initials against each declaration on the last page, print their name, and then sign and date in the relevant section. The person explaining the consent and Investigator should also print their name, and then sign and date the consent form. Provide the subject with a copy of both forms, and keep the original ICF in the subject's CRF Booklet.
- ii. The Investigator or a clinical assistant will review instructions and warnings for lens wear. Participants who appear unable or unwilling to follow instructions will not be enrolled onto the study.

- iii. The subject is assigned with a Subject ID number according to the Enrolment Log. Subjects must be enrolled sequentially. Enter details on Enrolment Log as outlined on the form, and onto the subjects Source Document Record (see Section 13.5 for further details).
- iv. Full ocular health will be established.

8.2.3 Baseline Assessment

The following baseline measurements and assessments will be recorded:

- i. Subject demographics, age, sex, medications, allergies
- ii. Monocular spherocylindrical refraction (sphere, cylinder and axis)
- iii. Monocular and binocular high contrast (HC) distance visual acuity (logMAR) with best spherocyl spectacle refraction [D]
- iv. Baseline Biometry measurements
 - Corneal topography: Sim-K-readings and corneal shape factor (Medmont)
 - HVID* (photo slit lamp)
 - Palpebral Aperture (mm)
 - Corneal sagittal height, corneal diameter (CD) (Visante OCT).
- * From photographs
- v. Slit lamp biomicroscopy
 - Limbal Hyperaemia (0-4)
 - Bulbar Hyperaemia (0-4)
 - Palpebral Hyperaemia (0-4) and roughness (0-4)
 - Corneal staining (0-4)
 - Conjunctival fluorescein staining (0-4)
 - Other findings (0-4).

See Appendix 6 for Grading Scales and measurement instructions.

Rinse away fluorescein with non-preserved saline (e.g. Sauflon saline) and allow at least 2 minutes for tear film to reform.

- vi. Complete the eligibility checklist.

The subject's eligibility will be assessed for the study ensuring that the subject meets all of the inclusion/exclusion criteria, and full ocular health must be established. If the subject is eligible, then they can be fitted with the study lenses, if not eligible, then the reason should be noted on the Enrolment Log and the Exit CRF should be completed before the subject exits from the study.

Enter the subject number on to the next line of the Randomisation Log to identify the first pair of study lenses.

8.2.4 1st Pair Study Lens Assessment

- i. Complete the Product Dispensing Foil Log.
- ii. Record the parameters of the lenses on the 1st Pair Study Lens Assessment CRF (lens code, lens power). Lenses powers should be chosen as close as possible to the subject's spherical refraction based upon habitual contact lens information and refraction.

- iii. Confirm lens is undamaged (Y/N). If yes, replace and complete Product Dispensing Foil Log.
- iv. Insert 1st pair of study contact lenses.
- v. Confirm subjects comfort and vision is satisfactory (Y/N). If no, then remove, replace and complete Product Dispensing Foil Log, and then repeat section v.
- vi. If yes, allow approximately 30-45 minutes settling period.
- vii. After settling, record the following on the 1st Pair Study Lens Assessment CRF:
 - Lens Fit
 - Horizontal* & vertical* centration / overlap (mm)
 - Post-blink movement in primary gaze (mm)*
 - Version lag (mm)
 - Edge tightness (0-4)
 - Tightness on push-up (%)
 - Diameter acceptance (mm)
 - Overall fit acceptability (0-5) and reason if Grade 2 or less
 - * From photographs / video
- viii. Remove 1st Pair Study Lenses and discard.
- ix. See Appendix 6 for grading scales and measurement instructions.

8.2.5 2nd Pair Study Lens Assessment

Repeat the procedure listed in 8.2.4 using the Product Dispensing Foil Log and 2nd Pair Study Lens Assessment CRF to record the clinical test variables for the second pair of study lenses.

8.2.6 3rd Pair Study Lens Assessment

Repeat the procedure listed in 8.2.4 using the Product Dispensing Foil Log and 3rd Pair Study Lens Assessment CRF to record the clinical test variables for the third pair of study lenses.

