4.2 Investigator Recruitment

The Investigators will be required to fulfil the following criteria:

- General Optical Council (GOC) registered optometrist
- At least two years post-registration contact lens fitting experience
- Experienced investigators trained in Good Clinical Practice (GCP)
- Willingness to follow the study protocol and to co-operate with the study monitors

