6.6 Product Accountability

Product Accountability and Dispensing Foil Logs will be kept by each site (Appendix 3 and 4). Number of lenses received (listed by power and lot number) and number of lenses used (even if not dispensed) will be recorded on these logs.

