01 / 09 /		/ /	Y/N	Y/N	
01 / 10 /		/ /	Y/N	Y/N	
01 / 11 /		/ /	Y/N	Y/N	
01 / 12 /		/ /	Y/N	Y/N	
01 / 13 /		/ /	Y/N	Y/N	
01 / 14 /		/ /	Y/N	Y/N	
01 / 15 /		/ /	Y/N	Y/N	
01 / 16 /		/ /	Y/N	Y/N	
01 / 17 /		/ /	Y/N	Y/N	
01 / 18 /		/ /	Y/N	Y/N	
01 / 19 /		/ /	Y/N	Y/N	
01 / 20 /		/ /	Y/N	Y/N	

TRTN-501

SAMPLE RANDOMISATION LOG

Subjects should only be entered onto the Randomisation Log once they have been found to be eligible for the study.

Subject ID Site /Sub/Initials	Randomisation Date (dd/mm/yy)	Pair 1	Pair 2	Pair 3
01 / 01 / JS	10/08/17	A	B	C
01 / 01 /		A	C	B
01 / 02 /		B	A	C
01 / 03 /		A	C	B
01 / 04 /		B	C	A
01 / 05 /		A	B	C
01 / 06 /		C	B	A
01 / 07 /		C	B	A
01 / 08 /		A	C	B
01 / 09 /		B	C	A
01 / 10 /		C	A	B
01 / 11 /		A	C	B
01 / 12 /		C	B	A
01 / 13 /		A	B	C
01 / 14 /		B	A	C
01 / 15 /		C	A	B
01 / 16 /		B	C	A
01 / 17 /		A	B	C
01 / 18 /		C	A	B
01 / 19 /		B	C	A
01 / 20 /		A	B	C

APPENDIX 3

Template Product Accountability Log

(1 Page sample only)

APPENDIX 4

Template Product Dispensing Foil Log

(1 Page sample only)

**TRTN-501
PRODUCT DISPENSING FOIL LOG**

Date/Page: _____/____ Investigator's Initials: _____ Subject ID: __/____/____

Please affix the OD and OS foil from the dispensed study lenses to the table below and record the applicable information. After each lens foil is affixed to the page the site staff member dispensing the lenses should initial and date the entry in the space provided in the middle column.

OD Foil	Visit Information	OS Foil
	Lens Code _____ Are Additional lenses Needed:  Yes  No If yes please affix foils below.	
OD Foil	Visit Information	OS Foil

SAMPLE ONLY DO NOT USE
	Lens Code _____ Are Additional lenses Needed:  Yes  No If you please affix foils below	
OD Foil	Visit Information	OS Foil
	Lens Code _____ Are Additional lenses Needed:  Yes  No If yes please affix foils below.	
OD Foil	Visit Information	OS Foil
	Lens Code _____ Are Additional lenses Needed:  Yes  No If yes please continue on next page of log.	

APPENDIX 5

Grading Scales & Measurement Instructions

GRADING & MEASUREMENT SYSTEM (TRTN-501)

VARIABLE	ASSESSMENT METHOD	GRADING/MEASUREMENT SYSTEM
Vision		
Distance VA – High contrast	Assessed using computer generated logMAR chart.	logMAR visual acuity (VA) to nearest letter.

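### The lens check before insertion (Protocol 8.2.4, step iii) has its trigger reversed: it replaces an intact lens and gives no action for a damaged one

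*Protocol*

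**What the plan says.** Section 8.2.4 of the protocol sets out the procedure for the first pair of study lenses as a numbered list. After the foil log has been completed (step i) and the lens parameters recorded (step ii), step iii reads: "Confirm lens is undamaged (Y/N). If yes, replace and complete Product Dispensing Foil Log".

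Step iv follows with no condition attached: "Insert 1st pair of study contact lenses". Step v is a second yes/no check, made once the lenses are on the eye: "Confirm subjects comfort and vision is satisfactory (Y/N). If no, then remove, replace and complete Product Dispensing Foil Log". Step vi then gives the yes branch of step v, which is to let the lenses settle.

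The other two pairs have no text of their own for this check. Section 8.2.5 says "Repeat the procedure listed in 8.2.4 using the Product Dispensing Foil Log and 2nd Pair Study Lens Assessment CRF", and section 8.2.6 says "Repeat the procedure listed in 8.2.4 using the Product Dispensing Foil Log and 3rd Pair Study Lens Assessment CRF".

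**The concern.** The question in step iii is framed positively: yes is the good answer. The action attached to yes is the one that belongs to the bad answer. Followed to the letter, the site discards an intact lens, and a damaged lens passes to insertion because nothing is said about what to do with it.

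Two things are at stake. One is subject safety, since this is the only lens-integrity check stated before insertion. The other is the fit assessment itself: a damaged lens left in place would be graded as though it represented its design. Both depend on someone following the sentence literally, which is unlikely, but an operative step should not rely on the reader to reverse it.

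**Working it through.** There is no figure in the plan to reproduce. The check is a reading of the branches, a comparison with the neighbouring step, and a search for text elsewhere that would correct the sentence.

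**1. Branches of the two checks in 8.2.4**

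| Step | Meaning of yes | Action on yes | Meaning of no | Action on no |
|---|---|---|---|---|
| iii (before insertion) | lens intact | replace, complete foil log | lens damaged | none stated; step iv inserts |
| v (after insertion) | comfort and vision satisfactory | settle (step vi) | not satisfactory | remove, replace, complete foil log, repeat the check |

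Both questions have the same form: confirm a favourable state, yes or no. Step v ties replacement to the unfavourable answer and step iii ties it to the favourable one. They cannot both be as intended, and step v is the one that makes sense.

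**2. Text elsewhere that might correct step iii**

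- Section 6.5 (Lens Replacement Schedule) deals with complications that a subject experiences with the lenses, not with a lens found damaged beforehand.
- Section 6.6 (Product Accountability) says that the "number of lenses used (even if not dispensed) will be recorded on these logs". It counts lenses but does not say when to replace one.
- The foil log template in Appendix 4 asks "Are Additional lenses Needed" and gives no criterion.
- Sections 8.2.5 and 8.2.6 refer back to 8.2.4 and so carry the error forward.

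None of these gives the correct rule.

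**3. How many lenses the step covers**

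Inputs: 2 lenses per pair (bilateral wear), 3 pairs per subject (section 3), 40 to 60 subjects (section 5.1).

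- Per pair: 2 × 40 = 80 to 2 × 60 = 120 lenses.
- All three pairs: 3 × 80 = 240 to 3 × 120 = 360 lenses.

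The protocol gives no rate of damaged lenses, so an expected number of affected lenses cannot be calculated.

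**The case against.** The strongest reply is that this is a one-word slip whose meaning nobody would miss. The literal reading defeats itself: if every intact lens were replaced, its intact replacement would have to be replaced too. The foil log has already been completed at step i, so a further entry makes sense only for an exception. The correct pattern stands two steps later.

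Several safeguards also exist. Section 4.2 requires registered optometrists with "At least two years post-registration contact lens fitting experience". The lenses are CE marked and come sterile in single-use packs. A lens that is uncomfortable or gives poor vision is removed at step v. Lenses used are logged whether or not they are dispensed. It is unknown whether the answer to step iii is recorded at all, because the case report form is not shown.

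Most of this stands, and it limits the weight of the point. It does not make the sentence right. Step v comes after insertion and tests comfort and vision, so it would not catch every defect. Section 13.3 bars investigators from departing from the protocol without written ethics approval and an amendment, yet the sensible action here departs from the text as written. Section 13.6 provides for no external monitoring, so no outside monitor would be there to notice different handling at the two sites.

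**Conclusion.** The concern holds. Step iii of section 8.2.4 attaches replacement to the wrong answer and leaves a damaged lens without an instruction. The error applies to all three pairs, 240 to 360 lenses in total, and nothing else in the protocol corrects it.

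The conclusion rests on the wording alone and needs no statistical assumption. Its practical weight is low: literal compliance is unlikely, and no effect on recorded data, the fit variables, the sample size or the analysis is shown. It is a drafting error in an operative step that bears on subject safety, to be corrected at the lowest level of priority.

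**What to change.** In section 8.2.4, step iii, make replacement follow a no instead of a yes. For example: *Check each lens before insertion. Is it undamaged (Y/N)? If no, replace it and complete the foil log before going on to step iv.* Equally good is to ask whether the lens is damaged and keep yes as the trigger.

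Because 8.2.5 and 8.2.6 point back to 8.2.4, this single edit covers all three pairs. If the case report form has a matching field, check that its wording agrees.

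The cost is one word plus ordinary version control, since section 13.2 ties ethics approval to document version dates. Design, sample size, endpoints and analysis are unchanged.

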8.2.7 Study Exit

The Study Exit Form must be completed for all subjects, who have signed the informed consent, to exit the study. This will occur either at study completion, i.e. after 3rd Study Lens Assessment, or when a subject is discontinued from the study. The exit date should also be recorded on the subjects named patient notes i.e. the Source Document Record.

Post-study follow-up visits will be scheduled if the Investigator judges this is necessary, but the Exit CRF must not be completed until any such visits have been completed.

At the study Exit Visit the following measurements are taken:

- i. Monocular sphero-cylindrical refraction (sphere, cylinder and axis)
- ii. Monocular distance visual acuity with sphero-cylindrical refraction (Snellen or logMAR).
- iii. Slit lamp examination
 - Limbal Hyperaemia (0-4)
 - Bulbar Hyperaemia (0-4)
 - Palpebral Hyperaemia (0-4) and Roughness (0-4)
 - Corneal staining (0-4)

- Conjunctival fluorescein staining (0-4)
- Other findings (0-4).

See Appendix 5 for grading scales and measurement instructions.

Rinse away fluorescein with non-preserved saline (e.g. Sauflon saline).

- iv. Post-study follow-up requirement (Y/N). If yes, the reason and date of the follow-visit must also be recorded.

If the subject is being exited due to discontinuation, further details need to be recorded on the exit form. This is described in Section 8.3 below.

8.2.8 Clinical Variables

The following table summarises the clinical measurements to be taken at each stage of the study:

Table 2: Summary of clinical assessments by visit

Procedure	Screening/ baseline	Pair 1 lens assessment	Pair 2 lens assessment	Pair 3 lens assessment	Exit
Subject demographics	✓				
Subject eligibility	✓				
Monocular spherocylindrical refraction	✓				✓
Monocular HCVA	✓				✓
Biometry- Medmont	✓				
Biometry- Visante OCT	✓				
Slit lamp biomicroscopy	✓				✓
Lens fit and comfort assessment		✓	✓	✓	

8.3 Subject Discontinuation

Subjects may be discontinued from the study at the discretion of the Investigator or the subject.

In the event of discontinuation, the Study Exit Form must be completed and the study exit date recorded on the Source Document Record. The Investigator will indicate the primary reason for discontinuation by ticking one of the boxes provided on the bottom half of the Exit Form. Further details can be provided in the ‘comments’ section if necessary.

8.4 Post-Study Follow-up

A post-study follow-up visit must be scheduled if the subject exhibits any slit lamp findings which are clinically different from baseline upon discontinuation or completion of the study, unless the Investigator judges that no follow-up is warranted.

Post-study follow-up visits will be recorded on the Unscheduled Visit CRF. All variables listed on the forms must be completed unless the subject exhibits a condition that prohibits their completion. If this is the case, a written explanation is required in the comments section.

The study Exit form should not be completed until all post study follow-up visits have been completed.

9 **ADVERSE EVENTS**

An Adverse Event (AE) is defined as any unfavourable or unintended sign (including an abnormal finding), symptom or disease temporarily associated with the use of a study device whether or not related to the study device. All AEs, both ocular and non-ocular (but related to the test or control lens or to the study procedures), will be monitored.

The Investigator will be required to judge whether or not an AE is device-related. In the case where more than one diagnostic finding is associated with an AE, the event will be counted as one event and categorized under the most significant of the findings.

The Investigator will be required to report all device-related AEs to the REC. The seriousness of an AE is categorized as being either serious, significant, or non-significant:

- Serious – Any untoward medical occurrence that results in death, is life-threatening, requires hospitalization or prolongation of existing hospitalization, results in persistent or significant disability/incapacity or is a congenital anomaly/birth defect.
- Significant – Symptomatic and warrant discontinuation of contact lens wear (temporary or permanent).
- Non-Significant – Usually asymptomatic and do not warrant discontinuation of contact lens wear (temporary or permanent). However, as a precautionary measure, the Investigator may decide to take action.

For additional information, questions, or assistance in recording potential AEs, the Investigator should refer to VCR Standard Operating Procedure for Good Clinical Practice (SOP-GCP-161).

9.1 Adverse Event Categorisation

The Investigator will be required to rate the likelihood of an event being lens-related (Possible, Probable, Highly Probable) or non-lens-related (No, Doubtful) in their adverse event evaluation.

9.2 Adverse Event Reporting

Upon discovery of an AE, the Investigator will complete an Adverse Event Form (AE form) to capture the event.

If applicable, the Investigator will notify the REC as per the REC requirements.

9.3 Device-Related Adverse Event Documentation

Investigators are required to document and follow-up all adverse events.

All adverse events are documented on an AE Form (Appendix 1) upon event discovery. For all ocular AEs, one AE form is used per eye. For AEs which are non-ocular but related to the study device (test or control) or to the study procedures, only one AE Form needs to be completed per AE.

Procedure:

The Investigator has the responsibility to:

1. Complete as much information as possible on the AE Form upon event discovery. This includes:
 - A detailed description of the adverse event and a diagnosis, including a probable cause.
 - Detailed drawings that detail size, location and depth, or photographs (if necessary).
 - Likelihood of the adverse event being device-related.
2. If appropriate, report the AE to the Research Ethics Committee within the specified timelines (see Reporting of Adverse Events section 9.2).
3. Follow study subject until resolution recording all information on an unscheduled visit CRF, including VA, symptoms and slit lamp findings, resolution and permanent sequelae if any.
4. Complete all remaining information as required on the AE Form. If follow-up of the adverse event is required, the resolution of the AE can only be completed when all follow-up visits are done. The following additional information will also be completed on the AE resolution form:
 - Outcome, ocular sequelae if any
 - Whether the patient is discontinued from the study as a result of the AE

9.4 Adverse Event Follow-up

The Investigator will conduct follow-up examinations until the condition has either: returned to pre-event status, stabilized, or been satisfactorily explained.

If the subject is referred for medical attention, they will be tracked by the Investigator until the aforementioned conditions are met.

Follow-up data will be collected on Unscheduled Visit CRFs and on the AE Form.

9.5 Study Completion

The study is completed when all subjects have completed the third pair study lens assessment or have been discontinued.

10 DATA MANAGEMENT

10.1 Data Quality Assurance

Before the final closing of the database, the data will be checked and any subsequent omissions and discrepancies resolved before analysis as per VCR SOPs.

10.2 Data Entry and Storage

Data shall be completed on the CRFs and hand entered into a database using DACs software and then exported to an Excel database (Microsoft). The statistical analyses will be completed using SAS software.

11 **SAMPLE SIZE AND STATISTICAL METHODS**

11.1 Sample Size Rationale

A sample size of 60 subjects showing a 90% success rate would give an 80% confidence interval of $\pm 5.0\%$. This would statistically differentiate success rates of 85% and 95%.

A sample size of 60 is sufficient to detect a mean difference of 5 (0-100) in tightness, or 0.2 mm in corneal overlap assuming the standard deviation of the mean differences in Table 2 below and assuming $\alpha=0.05$ with a power of 95%.

Table 2: Sample Size Justification:

	Sample Size	
	Tightness (0-100)	Corneal overlap (mm)
Mean of paired difference	5	0.2
SD of paired difference	10	0.4
Minimum sample size per group	42	42

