2.1 Hypotheses

The following hypotheses will be tested:

- i. The fitting success rate for a combination of two senofilcon A designs is greater than for a single design when fitted to a population skewed to larger corneas.
- ii. The fitting success rates for senofilcon A designs are equivalent to those predicted by the Young model.
- iii. The fitting characteristics (tightness, corneal overlap) for senofilcon A designs are equivalent to those predicted by the Young model.

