11.2 Level of Statistical Significance

The overall type I error rate will be preserved at 5%. To preserve type I error control, the study hypotheses will be evaluated using a sequential gate-keeping strategy. All tests will be two-sided. The three co-primary hypotheses will be simultaneously evaluated using $\alpha=0.05$, all of which must be met in order to satisfy the primary objective of this study.

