11.5.2 Success Rates – Actual versus Theoretical

Fit acceptance (0=Unacceptable, 1=Acceptable) will be analysed using a generalized linear mixed model with a binary distribution and a logit link function. Lens type, period, and the lens by period interaction will be included as fixed effects and subject will be included as a random effect. The proportion of eyes with acceptable lens fit with each lens type will be calculated with 95% confidence intervals. These confidence intervals will be compared to the theoretical success rates.

If the incidence rate is too low or there are problems with the convergence of the above model, the method of Wilson⁵ will be used to evaluate the confidence intervals.

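### Section 11.1 rests its only success-rate sizing claim (85% versus 95%) on an 80% confidence interval, while the trial works at two-sided 5% and 95% intervals

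*Protocol*

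**What the plan says.** Protocol section 11.1 gives one sizing statement for success rates: "A sample size of 60 subjects showing a 90% success rate would give an 80% confidence interval of" ±5.0%. The next sentence draws the conclusion: "This would statistically differentiate success rates of 85% and 95" per cent. Nothing else is offered in support, and the two rates are exactly the ends of 90% ± 5 points.

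The following paragraph of 11.1 turns to the continuous measures ("A sample size of 60 is sufficient to detect a mean difference of 5 (0-100) in tightness", or 0.2 mm in corneal overlap). It uses α = 0.05 and a stated power of 95%, which do not extend to success rates.

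Elsewhere the level is fixed as follows:
- Section 11.2: "The overall type I error rate will be preserved at 5"%, and "All tests will be two-sided".
- Section 11.5.2: "The proportion of eyes with acceptable lens fit with each lens type will be calculated with 95% confidence intervals", and "These confidence intervals will be compared to the theoretical success rates".

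Section 5.1 plans about 50 subjects, within a range of 40 to 60. Section 3.1 has every lens type worn in both eyes of every subject.

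**The concern.** An 80% interval corresponds to a two-sided 5% test no better than a two-sided 20% test does. Section 11.1 therefore justifies its success-rate claim at a looser level than sections 11.2 and 11.5.2 apply, and looser than its own next paragraph. It gives no reason for the change.

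This is the only sizing offered for success rates, on which hypotheses i and ii rest. Hypothesis i is the main one: "The fitting success rate for a combination of two senofilcon A designs is greater than for a single design". An ethics committee or other reader would take it that 60 subjects separate 85% from 95% at the trial's own 5% level. The reasoning given does not show that. What is at stake is how the trial's precision is represented; no analysis or decision rule uses the sentence.

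**Working it through.** **Inputs from the protocol.** Success rate p = 0.90 and n = 60 (11.1); 80% confidence (11.1); 95% confidence (11.5.2); two-sided α = 0.05 (11.2); 40 to 60 subjects (5.1); two eyes per subject (3.1). The protocol gives no between-eye correlation and no discordance rate, so those values below are assumptions.

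**1. Reproduce the stated figure.** Wald half-width = z × √(p(1−p)/n). The standard error is √(0.9 × 0.1/60) = 0.03873. At 80%, 1.2816 × 0.03873 = 4.96 points, which rounds to the stated 5.0. The formula and the arithmetic are confirmed.

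**2. Same formula at 95%.** 1.960 × 0.03873 = 7.59 points, counting one unit per subject as 11.1 does.

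**3. Allow for two eyes.** With between-eye correlation ρ, the effective number of units is 2n/(1+ρ). This runs from n (ρ = 1) to 2n (ρ = 0).

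| Subjects | 80%, one unit per subject | 95%, one unit per subject (or ρ = 1) | 95%, eyes fully independent |
|---|---|---|---|
| 60 | ±4.96 | ±7.59 | ±5.37 |
| 50 | ±5.44 | ±8.32 | ±5.88 |
| 40 | ±6.08 | ±9.30 | ±6.57 |

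As an intermediate case, ρ = 0.5 at 60 subjects gives 120/1.5 = 80 units and ±6.57. The 95% half-width is above 5.0 in every cell. Counting subjects, even the 80% half-width is within 5.0 only at the top of the enrolment range.

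**4. Units needed for ±5.0 at 95%.** 1.960² × 0.09/0.05² = 138.3, so 139 independent units. Sixty subjects supply at most 120.

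**5. Could the design still separate the rates?** Three checks, none of them in 11.1:

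- *Observed rate against the other rate.* At n = 60, the 95% Wilson interval (Wilson is the protocol's fallback method) is 73.9–91.9% for 51/60 (85%) and 86.3–98.3% for 57/60 (95%). Each excludes the other rate.
- *Power of that one-sample comparison at n = 60.* The Wilson interval lies below 95% when there are 53 or fewer successes, which has probability 82% if the true rate is 85%. It lies above 85% when there are 57 or more, which has probability 65% if the true rate is 95%. At n = 40 the figures are 74% and 40%.
- *Paired contrast (McNemar).* Assume nested outcomes: 10% of units succeed with the better option only and none with the other only, one unit per subject. The exact test needs at least 6 discordant units (2 × 0.5⁶ = 0.031). The asymptotic test needs at least 4 (z = √4 = 2, p = 0.046). From the binomial distribution with rate 0.10, power is 56% exact and 86% asymptotic at 60 units, and 21% and 58% at 40. With 120 independent eyes it is 98% and 99.8%.

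**The case against.** The strongest reply is that an interval centred on 90% does not test whether 85% and 95% can be told apart. Section 11.5.2 compares the interval around the observed rate with a theoretical rate. On that rule, observed rates of 85% and 95% are each separated from the other at 60 units. For hypothesis i, if a combination counts as a success when either lens fits and the single lens belongs to the pair, outcomes are nested by construction, so the favourable paired case is the natural one. All of this stands. It shows that the sentence may be true on other grounds, but not that the grounds given support it. Separation of observed rates is also not the same as adequate power.

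A reader might infer that the 95% interval around 90% always contains both rates, whatever the between-eye correlation. The protocol does not support this. The Wald interval for 120 independent eyes, 84.6–95.4%, does contain both. The Wilson intervals for 80, 100 and 120 independent eyes (81.5–94.8%, 82.6–94.5%, 83.3–94.2%) contain 85% but exclude 95%. Nor is ±7.6 the trial's precision without qualification. Section 11.5.2 analyses eyes, and ±7.6 is the fully correlated end of the range.

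A last reply is that the 80% level is openly stated and the ±5.0 is right. That is so, and there is no arithmetic error. But disclosing the level does not make the conclusion hold at the level at which the trial tests.

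**Conclusion.** The point holds as a mismatch of confidence level that leaves a sizing claim unsupported, and the passage is wrong as written. At the trial's 95% level the Wald half-width at 90% success is ±5.4 to ±7.6 points for 60 subjects, ±5.9 to ±8.3 for 50 and ±6.6 to ±9.3 for 40, against the stated ±5.0. The lower ends assume fully independent eyes; the upper ends assume fully correlated eyes or one unit per subject.

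It would go too far to infer that 60 subjects cannot separate 85% from 95%. Power for that ranges from 56% to 86% in the nested paired case with one unit per subject, and is higher if second eyes add information. The answer turns on discordance, between-eye correlation and choice of test, none of which 11.1 states.

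**What to change.** Change two sentences in section 11.1.

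1. Replace the precision statement with one at the trial's level, for example: at 90% success the 95% confidence interval is about ±7.6 points with 60 subjects, ±8.3 with 50 and ±9.3 with 40, counting one unit per subject, or ±5.4, ±5.9 and ±6.6 if both eyes were fully independent.
2. Delete the sentence on differentiating 85% from 95%, or replace it with a paired calculation at two-sided α = 0.05 that states its assumed discordance and between-eye correlation.

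Enrolment, analyses and decision rules stay as they are. The cost is a less favourable stated precision and, if the differentiation claim is kept, the need to write down and defend the paired assumptions.
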